### ***Screening***

Individuals who indicate that they are interested in potentially participating will first be brought to the REDCap Screener Introduction. At this point, they will be asked if they want to be screened for study eligibility. Those who screen eligible for the study and are interested in study participation will be asked for contact information. No further data will be collected from those who screen ineligible or state they are not interested in study enrollment. The screening process will take approximately 5-10 minutes.

### ***Informed Consent***

Individuals who meet eligibility criteria, indicate that they want to participate in the study, and provide their contact information will be emailed a link to the REDCap study informed consent form within one business day of completing the screener. The VCU IRB granted a waiver for signed informed consent. This consent form describes the purpose of the study, involvement in the study (e.g., randomization to two study groups, completion of daily surveys for 28 days, baseline and follow-up assessments, compensation, etc.); the voluntary nature of the study; limits of confidentiality; as well as risks, benefits, and costs of participation. Additionally, participants will be told that they could stop participation at any point without negative repercussions. Participants select one of the following options: "Yes, I understand this and want to participate in the PROMOTING MONITORING: A PILOT TEST study" or "No, I do not want to participate in the study." Those who provide consent to participate in the study will proceed to baseline assessment, followed by randomization to either the contingency management (CM) or control (Co) group.

### ***Baseline Assessment***

Following informed consent, participants will complete a series of computer-administered questions via REDCap (demographic information; medical and mental health history; The Brief Pain Inventory; Pain Self-Efficacy Questionnaire; Pain Catastrophizing Scale; Hospital Anxiety and Depression Scale; Pittsburgh Sleep Quality Index; and 28-day Timeline Followback). Baseline assessment will take approximately 30-45 minutes to complete. If participants do not complete the baseline survey within two days of completing the screener, they will be sent a reminder email to complete the survey. If participants do not complete the baseline survey within three days post screening, they will be called. At the end of their baseline survey, participants will be asked their preference for a 5-10-minute telephone or Zoom call to finish their baseline visit. They will then be informed that within the next business day they would receive a call or email from study staff to set up their Zoom or phone appointment to complete the baseline visit. Participants will be called daily for one week following baseline survey completion until they are reached to complete the baseline call. Participants who can not be reached by telephone or Zoom within one week of completing the baseline survey will not be enrolled or randomized into the study.

### ***Baseline Visit Call***

During the 5-10-minute Zoom or telephone call RAs will review the following with all study participants: verify study eligibility; complete randomization to CM or Co groups; set up the DynamiCare Rewards app on the participant's smartphone; and remind them that they would receive daily text message reminders to complete the daily survey. RAs also will encourage participants to set an alarm or some other reminder of their own. In addition, for participants randomized to the CM condition, RAs will review CM procedures, including their debit card,

and they explain that they will receive an initial draw and reward for setting up the app.

Participants will also be offered handouts summarizing the information discussed in the call.

**Randomization.** Participants who complete the baseline visit call and are verified as eligible for the study will be randomly assigned to either the CM ( $n = 46$ ) or Co ( $n = 35$ ) condition. To determine group assignment, study staff will use an Excel spreadsheet with randomization groups determined by a random numbers app and prepared by [name] in advance of study launch. Each row with a randomization group will be numbered sequentially and correspond to a participant's study ID number. Study staff will not see the randomization group until they indicate that the participant is enrolled in the study and ready to be randomized. No stratification variables are proposed for this Stage I pilot study (see Rounsville et al., 2001).

**DynamiCare Rewards App.** DynamiCare is an iOS and Android app which fully automates CM methodology. The app will be customized for the present study, incorporating the daily self-monitoring survey and incentives plan. After randomization, all participants will be added to the DynamiCare Analytics portal and received an email with the link to download the app on their smartphone. Once participants successfully downloaded the app, RAs instructed them in the use of the app.

**All Participants.** Day 1 of the daily surveys will start the day after the app is downloaded and the account is set up. Participants will be encouraged to complete the daily survey and pick a time of day to set a personal reminder. They will receive a text reminder around noon each day from a study smartphone. The daily survey data will automatically be uploaded to the DynamiCare HIPAA-compliant server. Participants' DynamiCare Rewards accounts will be manually archived after they completed the 28-day survey period.

**CM Group.** Participants randomized to the CM group will have the chance to receive incentives for complying with the target behavior (completing daily self-monitoring surveys within a 12-hour window (8am-8pm) over a 28-day period. Daily self-monitoring surveys and the delivery of incentives were completed using the DynamiCare Rewards app. The escalating variable-ratio reinforcement schedule used for the study was modeled after the fishbowl method developed by Petry et al. (2005a) and Olmstead and Petry (2009).

Behavioral incentives will be managed remotely via the app to facilitate extrinsic motivation for participant follow-through with self-monitoring. Participants will be able to draw from a fishbowl via the app to determine their monetary prize. Participants will be given an initial draw for downloading the app and completing training during the baseline call, which will be set to \$8. When they meet the target behavior, participants will be awarded additional draws through the app. The number of draws they earn will increase by one for every day they completed the survey. The maximum number of draws they could earn over the course of the 28-day period was 236. Failure to complete a daily self-monitoring survey, however, resulted in a reset to baseline (1 draw per completed daily self-monitoring survey) and 3 consecutive completed daily self-monitoring surveys will be required for a participant to return to the highest level achieved prior to reset. Additional engagement with the app will not result in additional monetary reinforcement.

***Incentives.*** Specifically, reward amounts ranged from \$0-50 in value. Half (50%) of incentives will be “good job” and not associated with a monetary reward. The app will be connected to reloadable debit cards (The Next Step debit card, provided by True Link Financial, Inc.), which will be activated and mailed to CM participants within one to two weeks of their baseline call.

**Co Group.** The Co group will be asked to download the DynamiCare Rewards app during the baseline visit call and to complete the same daily self-monitoring survey as the CM group, but will not be provided with incentives for completing the survey. They also will receive the same reminders to complete the daily survey as the CM group. The only difference between the CM and Co groups will be the receipt of incentives for the 28-day trial.

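### The call sequence appears to put the shared reminder and alarm coaching after the arm is known, and the plan is inconsistent about when randomization happens

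*Combined protocol and SAP*

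**What the plan says.** All of this sits under Baseline Visit Call in the combined protocol and SAP.

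- The call is introduced with "During the 5-10-minute Zoom or telephone call RAs will review the following with all study participants". The tasks then listed are "verify study eligibility; complete randomization to CM or Co groups; set up the DynamiCare Rewards app on the" participant's phone, and finally to "remind them that they would receive daily text message reminders to complete the daily survey".
- The next sentence is "RAs also will encourage participants to set an alarm or some other reminder of their own".
- The CM-only content comes after that: "In addition, for participants randomized to the CM condition, RAs will review CM procedures, including their debit card".
- The Randomization paragraph says that assignment is made for people who have completed the call and been verified as eligible. It also says that staff cannot see the group until they mark the participant as enrolled and ready.
- The DynamiCare Rewards App paragraph places portal registration and the download link after randomization, with RA instruction once the app is installed.
- The Co Group paragraph has controls download the app during this same call. It closes with "The only difference between the CM and Co groups will be the receipt of incentives for the 28-day trial".

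**The concern.** Both primary outcomes, the number of surveys completed out of 28 days and the longest unbroken run, depend on remembering to do the survey. Choosing a time and setting an alarm bear directly on that. The coaching is meant to be common to both arms, so that any arm difference can be credited to incentives. If the person giving it already knows the arm, its emphasis can vary by arm without anyone intending it. The planned unadjusted t-tests could not separate such a difference from the incentive effect.

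This matters for a pilot because the Effect Size Estimation section makes the arm means and variances the main product, to be used in sizing a larger trial. Participants cannot be masked to incentives, but that does not require the reminder coaching to follow allocation.

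**Working it through.** The plan attaches no figure to this point, so the check compares the statements on timing.

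1. **Task list.** Eligibility, randomization, app set-up, text-reminder talk. The alarm sentence follows the list, and the CM-only review follows that. Nothing labels the list as a sequence, but it reads as one.
2. **App steps.** Portal entry and the download link come after randomization, and controls download the app during the call. Randomization must therefore take place within the call and before app instruction. The Statement of Problem and Aims gives the same order: baseline assessment, assignment, download and instruction.
3. **CM-only review.** This is also part of the call and is given only to those assigned to CM, so the arm must be known before the call ends.
4. **Randomization paragraph.** Taken literally, assignment follows a completed call. That cannot be squared with items 2 and 3.
5. **Alarm and text talk.** List order is the only evidence of when these are given relative to allocation. No statement places them before it, except the sentence in item 4, which conflicts with the rest.
6. **Safeguards.** Concealment until the participant is marked ready protects the assignment, not what is said afterwards. Handouts are offered, which standardizes content in part. No call script, masking of staff after assignment, or fidelity check is described.

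How unequal coaching would enter the estimate, in a simple additive form:

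observed mean difference = incentive effect + (coaching effect in CM − coaching effect in Co)

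The bracket is zero if the coaching is delivered equally. It is positive if CM participants are coached harder. It is negative if RAs compensate controls, or if the shared part is cut short in CM because the CM review must fit into the same 5-10 minutes. The documents supply no value for either term in the bracket, so no size can be computed. If CM participants act more on equal coaching because they are paid, that belongs to the incentive effect and is not at issue here.

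**The case against.** The strongest reply is that nothing here demonstrates a bias. The trial is an unavoidably open-label Stage I pilot. The task list is introduced as things to review, not as steps. The alarm sentence carries no time of its own, and the Randomization paragraph can be read as call first, allocation second. The coaching is one brief encouragement, backed by handouts, and survey data upload automatically, so outcome capture is unaffected. Most of this stands, and it limits the point to a low-priority clarification. It does not remove the point, because the app and CM-only steps show that allocation is opened during the call and the plan does not protect the reminder coaching from that knowledge.

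A reader might infer more than the text supports:

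- **One RA, aware of the hypothesis, does everything.** A single short call makes one RA plausible, but the plan says only that RAs conduct it. It does not say what they know of the hypothesis.
- **The daily text is a second route for unequal effort.** The plan says "They will receive a text reminder around noon each day from a study smartphone", under the heading for all participants, and the Co Group paragraph gives controls the same reminders as CM. Whether texts are typed or scheduled is not stated, and a study phone as the source is not evidence of a difference by arm.
- **The bias can be expressed as a standardized effect.** That would need an assumed shift in completion and an assumed standard deviation. The documents give neither, nor any basis for a shift above zero.

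**Conclusion.** The concern holds in a limited form. The plan appears to have RAs who know the arm give shared coaching that bears on both primary outcomes, and its statements on when randomization occurs conflict. This rests on reading the task list as a sequence, which the app and CM-only steps support and the Randomization paragraph contradicts. Unequal emphasis is possible, not shown, and its size and direction are unknown. The statement that incentives are the only difference between arms is the intended design. Nothing in the call description disproves it, but the call as ordered does not secure it for the reminder coaching. The point is minor and worth acting on because the remedy is nearly free.

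**What to change.** Reconcile the task list with the Randomization paragraph by stating one order for the call:

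1. Verify eligibility.
2. Give everyone a common script: the daily survey, the noon text, choosing a time of day and setting an alarm.
3. Open the allocation.
4. Set up the app, using the same instruction script in both arms.
5. Give the CM-only script.

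Reword the Randomization paragraph so that assignment follows steps 1 and 2, not the whole call.

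**Cost:** rewriting a 5-10-minute script, with no added contact or staff. A few minutes of coaching may go to someone who then declines randomization. App instruction remains unmasked because the download follows allocation. The common instruction script in step 4 limits discretion there but does not remove it.

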### ***Post-Daily Survey Period Follow Up***

At the end of the 28-day self-monitoring survey period, participants will be emailed a link to the REDCap follow-up survey (approximately 30-45 minutes), including The Brief Pain Inventory; Pain Self-Efficacy Questionnaire; Pain Catastrophizing Scale; Hospital Anxiety and Depression Scale; acceptability questions; Pittsburgh Sleep Quality Index; Timeline Followback (TLFB); and self-report validity and accuracy questions. If participants do not complete the survey within two days, they will be sent a reminder email. If participants do not complete the survey after three days, they will be called. Participants will be asked if they would like to be provided with a document summarizing their daily survey ratings in the follow-up survey. Once participants complete their participation in the study, we will remove their contact information from the study database to protect their privacy.

### ***Participant Compensation***

Participants will be compensated with a 20-dollar Amazon electronic gift card for completing the baseline visit and a 30-dollar Amazon electronic gift card for completing the follow-up survey. Electronic gift cards will be distributed via email within 1-2 weeks of completing their visit.

### **Measures**

Assessment measures were carefully selected, based on domains to be studied, psychometric properties of existing measures, previous research in this population, and personal experiences from preliminary studies with the target population. The battery will take approximately 30-45 minutes to complete. Screening, baseline, and follow-up data will be collected and managed using REDCap hosted at Virginia Commonwealth University. Table 3 provides an overview of measures and the baseline and follow-up surveys can be found in Appendix B.

#### ***Baseline Survey Only***

**Demographic Information.** Participants were asked about race, ethnicity, age, gender, marital status, employment status, highest grade completed in school, and living situation.

**Medical and Mental Health History.** Participants were asked about the number of days they experienced medical problems in the past 30 days; previous and current mental health and medical conditions; and if they were currently prescribed opioid, benzodiazepine, and other types of pain medications in the last 28 days.

#### ***28-Day Monitoring Period***

**Daily Self-Monitoring Survey.** Once daily, all participants were asked to complete a self-monitoring survey using the app, which was designed to take approximately 5 minutes to complete. Survey items were derived from validated measures and previously tested pain self-monitoring apps/electronic diaries and include the following domains: pain experience; impact of pain on function; sleep; mood; pain catastrophizing; prescription medication use (opioids and sedatives); alcohol use; marijuana use, cannabidiol (CBD) use (Cleeland & Ryan, 1994; Jamison et al., 2016; Finan et al., 2017; Watson et al., 1988; McNair et al., 1992; Sullivan et al., 1995).

See Appendix A for the complete daily self-monitoring survey.

**Mean Daily Self-Monitoring Survey Completion Time.** The app measured the time it took participants to complete the daily self-monitoring survey; all survey completion times were averaged.

### ***Baseline & Follow-Up Survey***

**Brief Pain Inventory (BPI; Cleeland & Ryan, 1994).** The BPI is a well-known measure of clinical pain and has demonstrated sufficient reliability and validity. This self-report questionnaire asks about pain history, severity, and its impact on functioning. Participants rate the intensity of pain at its worst from the past 24 hours, at its least from the past 24 hours, on average, and “right now” on a 0-10 scale. Participants also rate how much pain has interfered with various aspects of their life on a 0-10 scale.

**Pain Catastrophizing Scale (PCS; Sullivan et al., 1995).** The PCS is a 13-item measure of catastrophizing, including rumination, magnification, and helplessness. Each item is rated on a 0-4 scale. Item responses are summed to generate a total score; higher scores indicate increased pain catastrophizing. It has been found to have adequate reliability and validity (Osman et al., 1997).

**Pain Self-Efficacy Questionnaire (PSEQ; Nicholas, 1989; Nicholas, 2007).** The PSEQ is a 10-item measure of pain self-efficacy. Each item is rated on a 0-6 scale. Items are summed to generate a total score, with a greater total score indicating increased pain self-efficacy. The PSEQ has been shown to be reliable and valid (Gibson & Strong, 1996; Asghari & Nicholas, 2001).

**Hospital Anxiety and Depression Scale (HADS; Zigmond & Snaith, 1983; Bjelland et al., 2002).** The HADS is a widely used 14-item measure of past-week presence and severity of anxious and depressive symptoms. Response options range from 0-3. Two scores are summed

from the responses, a depression score and an anxiety score, with higher values indicating heightened experience of symptoms. The HADS has adequate reliability and validity, and an optimal balance between sensitivity and specificity.

**Pittsburgh Sleep Quality Index (PSQI; Buysse et al., 1989).** The PSQI is a reliable and valid measure of sleep quality and disturbances over the past month. The questionnaire contains 19 items focusing on subjective sleep quality, sleep latency, sleep duration, habitual sleep efficiency, sleep disturbances, use of sleeping medication, and daytime dysfunction.

***Follow-Up Survey Only***

**TLFB (Sobell & Sobell, 1992).** The TLFB is a widely-used, semi-structured interview that uses a calendar to retrospectively collect daily information about substance use. It has been shown to have good reliability and validity and is widely considered the “gold standard” of quantity and frequency substance use assessment. To accommodate the remote study procedures, the TLFB was adapted from interviewer to computer administered (via REDCap), which has been found to be reliable and valid (e.g., Martin-Willett et al., 2020). The TLFB was used to obtain detailed past 28-days frequency of opioid pain medication and alcohol use information.

**Acceptability.** Participants were asked to answer questions about satisfaction, acceptability, and feasibility on a 0-10 scale based on those used in a previous RCT investigating an app developed for chronic pain patients (Jamison et al., 2017).

**Validity and Accuracy of Responses.** All participants were asked how honest they were in completing the daily survey (response options: I was very honest, I was honest most of the time, I was honest some of the time, I was honest once in a while, I was not honest at all). CM participants were additionally asked how much the rewards made a difference in how accurately

they reported information in the daily survey (response options: Not at all, very little, little, somewhat, much, to a great extent, completely).

**Self-Report of Impact of Behavioral Incentives to Adherence.** CM participants were asked how much the rewards made a difference in whether they completed the daily survey (response options: Not at all, very little, little, somewhat, much, to a great extent, completely).

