## **Aims**

The specific aims of this Phase 1 therapy development project are to:

*Aim 1:* Compare number of completed daily self-monitoring surveys in CM and C groups. One hypothesis was tested:

*Hypothesis 1:* CM group participants will complete more daily self-monitoring surveys compared to control group participants.

*Aim 2:* Compare longest sustained period of daily survey completion in CM and C groups. One hypothesis was tested:

*Hypothesis 1:* CM group participants will have a longer sustained period of daily survey completion compared to control group participants.

*Aim 3:* Examine agreement between daily survey and follow-up visit reports of alcohol and Rx opioid use in CM and C groups.

*Aim 4:* Examine feasibility and acceptability of CM app implementation targeting self-monitoring of pain severity, related factors, and use of Rx opioids and alcohol.

*Aim 5:* Estimate effect-size to be used to perform power analyses and sample size calculations as part of the design of a larger RCT.

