### ***Outcome Measures***

As shown in Table 4, the primary outcome measures are the number of completed daily self-monitoring surveys and the longest period of sustained adherence to survey completion. It is hypothesized that those in the CM group will complete more daily self-monitoring surveys and have a longer sustained period of daily survey completion compared to controls. The number of completed daily surveys and duration of continuous daily survey completion will be compared between CM and Co groups using independent *t*-tests.

Secondarily, descriptive statistics will be used to summarize CM participants' self-report of the impact of behavioral incentives on adherence. Mean time to complete the daily surveys between CM and Co groups will be compared using an independent *t*-test. Pain experience and

related variables from baseline will be compared to follow up responses for the total sample using paired *t*-tests. The daily survey item responses will be summarized for the overall sample using descriptive statistics. Associations between daily survey and follow-up TFLB for alcohol and prescription opioid use data for the overall sample and each study group will be examined using Spearman's correlations. Descriptive statistics will be used to summarize self-report validity and accuracy of responses. Feasibility and acceptability of CM app implementation will be examined by comparing follow-up acceptability survey ratings for each group using independent *t*-tests.

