**Table 4**

*Outcome Measures Overview*

Name	Time Frame	Brief Description
Number of daily surveys completed	28-day daily survey period	This primary outcome is consistent with previous CM studies.
Longest period of sustained adherence to daily survey completion	28-day daily survey period	Largest number of consecutive days wherein daily surveys were completed. This primary outcome is consistent with previous CM studies.
Mean frequency of alcohol and prescription opioid use (days of use)	28-day daily survey period to follow up	Spearman's correlations between daily survey and TLFB data for alcohol and prescription opioid frequency (days of use) were conducted for the entire sample, the CM group, and the Co group.
Mean time to complete the daily surveys	28-day daily survey period	Daily survey completion time (the amount of time from daily survey start to finish).

Name	Time Frame	Brief Description
Mean CM app feasibility and acceptability survey ratings	Follow up	CM app satisfaction, acceptability, and feasibility survey ratings (on a 0-10 scale; administered at follow-up) based on those used in a previous RCT investigating an app developed for chronic pain patients (Jamison et al., 2017).
Self-report validity and accuracy of responses	Follow up	Ratings of how honest participants were in completing the daily survey and how much the rewards made a difference in how accurately CM participants reported information in the daily survey.

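### Aim 3 compares only totals of use days, so a high correlation between app and TLFB can coexist with disagreement about which days use occurred

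*Combined protocol and SAP*

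**What the plan says.** Aim 3 (Aims) reads: "Examine agreement between daily survey and follow-up visit reports of alcohol and Rx opioid use in CM and C groups". The Outcome Measures section gives one method for comparing the two sources, Spearman's correlation: "Associations between daily survey and follow-up TFLB for alcohol and prescription opioid use data for the overall sample and each study group". Table 4 fixes the unit of data: "Spearman's correlations between daily survey and TLFB data for alcohol and prescription opioid frequency (days of use) were conducted". Each person therefore contributes one count per source and substance.

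Both sources are described at a finer resolution than that:

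- **App** (28-Day Monitoring Period): "Once daily, all participants were asked to complete a self-monitoring survey using the app". The use items in Appendix A sit under a heading about the previous day.
- **TLFB** (Follow-Up Survey Only): an instrument that "uses a calendar to retrospectively collect daily information about substance use".

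No day-matched comparison is planned anywhere. The honesty and reward-accuracy questions at follow-up are self-ratings summarised descriptively. They do not compare the two records.

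**The concern.** A statistic computed on totals is unchanged when use days are rearranged within a person. If days left out of one source are offset by days added elsewhere, the totals match and the mismatch disappears. Replacing the correlation by a paired difference of totals, or aligning the two 28-day windows, would not change this.

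What is at stake is the reading of Aim 3. The day of use is what a daily survey adds to a 28-day count, and the protocol's rationale (Self-Monitoring; Remote Self-Monitoring) rests on frequent reporting being better than retrospective recall. A high Spearman coefficient could be reported as agreement when only the frequencies agree.

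**Working it through.** The documents give no figure for Aim 3 agreement and no use rates, so there is no stated result to reproduce. The only number taken from the plan is the expected follow-up sample: 80 recruited × 0.80 retained = 64 (Sample Size Justification). Everything else below is assumed.

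**1. One person.** Suppose each source reports k use days out of 28 and the days are placed independently.

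- Expected overlap = k²/28; expected contradictory days = 2(k − k²/28) = 2k(28 − k)/28.
- For k = 14: overlap 14 × 14/28 = 7, so 7 + 7 = 14 of 28 days contradict, while the totals differ by 0.

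**2. How far contradiction can go when totals are equal.** Minimum overlap is m = max(0, 2k − 28), and minimum day agreement is 1 − 2(k − m)/28.

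- k = 14: 0%
- k = 20: 1 − 16/28 = 43%
- k = 24: 1 − 8/28 = 71%
- k = 28: 100%

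The scope for contradiction therefore shrinks for near-daily users, and it is nil for never-users and daily users whose totals match.

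**3. Across a sample, equal totals, random placement.** The contradictory share is the mean of 2k(28 − k)/28². For k uniform on 1–27 the mean of k(28 − k) is 3654/27 = 135.3, giving 2 × 135.3/784 = 0.345. For k uniform on 1–14 it is 1925/14 = 137.5, giving 0.351. If k is binomial with person-level rate p, the share is 2·E[p(1 − p)] × 27/28.

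| Assumed use pattern | Calculation | Contradictory person-days |
|---|---|---|
| 50% never, 25% daily, 25% with 1–27 days | 0.25 × 0.345 | 8.6% |
| 40% never, 60% with 1–14 days | 0.60 × 0.351 | 21.0% |
| Rates Beta(0.5, 0.5) | 2 × 0.125 × 27/28 | 24.1% |
| Rates uniform on 0–1 | 2 × (1/6) × 27/28 | 32.1% |
| All with 1–14 days | 0.351 | 35.1% |
| Rates Beta(2, 2) | 2 × 0.20 × 27/28 | 38.6% |

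In every row Spearman's rho on totals is 1.00, because the totals were set equal.

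**4. Totals allowed to differ by ±1 day** (simulation, N = 64, all surveys completed, uniform rates).

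- TLFB days at random: rho 0.99, 32% contradictory, mean within-person kappa 0.00.
- TLFB days on the same dates: rho 0.99, 2% contradictory, kappa 0.87.

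The planned statistic cannot separate these two cases; a day-matched one can.

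**5. Missed surveys.** Here the app count is taken unadjusted from completed days (N = 64, 200 simulated datasets per setting). Ranges are over four patterns: 1–14 days, 0–28 days, and the two mixtures with never-users above.

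| Mean completion | rho, identical days | rho, minimum overlap |
|---|---|---|
| 80% | 0.914–0.975 | 0.914–0.976 |
| 50% | 0.715–0.944 | 0.716–0.945 |
| 33% | 0.538–0.889 | 0.535–0.895 |

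Rho falls with missed surveys, but by practically the same amount whether the two sources agree on every day or overlap as little as possible. It carries no day-level information in either case.

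**6. Why chance correction must be within person.** In the 0–28 day pattern with random placement, 68% of app use days are matched by chance and pooled kappa is 0.36, but mean within-person kappa is 0.00. Pooled figures partly reflect differences between people in how often they use.

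**The case against.** Four objections have weight.

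- **A reader might infer that contradictory reports will come out as near-perfect agreement.** The documents do not support that. It requires totals that rank alike and few missed surveys, and both were inputs to the illustrations. The protocol itself expects adherence to be a problem, and step 5 shows rho well below 1 when completion is poor. The supportable statement is that a high rho can coexist with day-level disagreement.
- **The size may be small.** Eligibility needs only one lifetime opioid prescription, so many participants may report no opioid use at all. In the first mixture of step 3, even minimum overlap leaves 87% day agreement and pooled kappa 0.73.
- **A reader might infer that Aim 3 demands day-by-day concordance, so that a day-level analysis must replace the planned one.** The aim does not say so. Table 4 names days of use, and the TLFB description ends with the study's own purpose: "The TLFB was used to obtain detailed past 28-days frequency of opioid pain medication and alcohol use information". Agreement on frequency is a coherent target. The TLFB relies on 28-day recall, so a day mismatch mixes recall error in the TLFB with inaccuracy in the app. This supports adding a day-level analysis, not substituting it.
- **By-date storage is not confirmed.** The calendar description is of the TLFB in general. The study adapted it for REDCap, and Appendix B does not reproduce that form.

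All four limit the point. None supplies the missing day-level comparison or lets a correlation of totals stand in for it.

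**Conclusion.** The point holds in a limited form. The only planned test of Aim 3 uses per-person totals, which cannot show whether the app and the TLFB name the same days, although the plan describes both as daily records. With matching totals and randomly placed TLFB days, contradiction runs from about 9% of person-days (mostly non-users and daily users) to about 39% (mostly intermediate use). That is a range over assumed patterns, not a bound or a forecast for this trial. The effect is largest for intermediate use and vanishes for people who never use or use every day. Missed surveys depress rho separately. Because the trial expects completion to differ by arm, a difference in rho between arms could arise from completion alone. Aim 3 is secondary in a Stage I pilot, and neither the primary outcomes nor the sample size changes.

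**What to change.** First, the sponsor should confirm that the REDCap TLFB is stored by date. If it is, add a day-level analysis to Outcome Measures and Table 4, beside the frequency comparison:

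- Pair each app survey dated t with TLFB date t − 1, because the survey asks about the previous day. Use only days with both records.
- For each substance, overall and by arm, tabulate yes/yes, yes/no, no/yes and no/no.
- Report positive agreement, 2a/(2a + b + c), and negative agreement, 2d/(2d + b + c), where a and d are the yes/yes and no/no counts and b and c the discordant ones.
- Report within-person kappa among people with some but not daily use. Kappa is undefined when both sources show no use, or use on every day.
- Give 95% confidence intervals bootstrapped by participant.

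Keep the days-of-use totals and Spearman's rho, and limit any conclusion drawn from them to frequency. If the TLFB is not stored by date, the day-level table is not possible and that same limit on the conclusion should be stated.

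The cost is SAP wording, a by-date export and a little more analysis; no new data are needed if dates are stored. TLFB date-recall error will make day-level agreement look less favourable than the correlation, so the two should be read together.
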